1.5. Clinical Data for Pamiparib

[figure not shown]
1.5.1. Pharmacokinetics of BGB-290-AU-002

In the first-in-human Phase 1 study, interim PK data of pamiparib showed that pamiparib is rapidly absorbed and eliminated after oral administration. The maximum serum concentration (C_{max}) and the drug exposure (the area under the concentration-time curve [AUC]) increased in a nearly dose proportional manner from 2.5 mg BID to 120 mg BID both after the single dose administration and at the steady state. The terminal half-life was determined to be approximately 13 hours, with a range of 5.4 to 34 hours. At the steady state, from 2.5 mg BID to 120 mg BID, drug exposure was increased in a dose-dependent manner, with an approximately 2-fold accumulation.

1.5.2. Exploratory Biomarker Data

The PAR formation from peripheral-blood mononuclear cells (PBMCs) was detected by ELISA to explore the dose-responsive PD activity in the Pamiparib Phase 1 monotherapy study. Blood samples for PK and isolation of PBMCs were obtained at baseline, on day 1 (pre-dose), and days 1 and 17 (4 hours post-dose) of Cycle 1 (Figure 4).

[figure not shown]
Figure 4: PAR inhibition was plotted against BGB-290 dose at the time of PBMC collection

PBMC = peripheral blood mononuclear cell

The PD activity at 4h post-dose on D1 and D17 were reported as percentage PAR inhibition from pre-dose. PD/PK correlation analyses were conducted from 30 patients who received doses of 2.5, 5, 10, 20, 40, 60, 80, and 120 mg BID. Robust PAR inhibition in PBMCs was observed even at the first dose level of 2.5mg BID, consistent with the clinical activity observed, and appeared to be maximal at doses ≥ 10 mg BID. The PD activity also increased in an exposure-dependent manner with sustained PAR inhibition in PBMCs being observed at steady state exposures expected in patients treated with 10 mg BID, or higher, doses (Figure 5, arrow).

Figure 5: PAR inhibition was plotted against BGB-290 drug level in the plasma at the time of PBMC collection

PBMC = peripheral blood mononuclear cell

1.5.3. Clinical Safety and Preliminary Efficacy for BGB-290-AU-002

BGB-290-AU-002 is a first-in-human study evaluating pamiparib to characterize the safety, MTD, preliminary anti-tumor activity, and the PK of pamiparib given as a monotherapy in a 3+3 dose escalation scheme. Pamiparib was administered in doses ranging from 2.5 mg orally (PO) BID up to 120 mg PO BID.

The study was conducted in 5 Australian study centers and preliminary data for 45 patients are available (cut-off date of 30 September 2016).

The preliminary safety data indicate the most frequent related AEs ($\geq 10\%$ of patients) assessed as related were nausea (58%, n = 26), vomiting (51%, n = 23), fatigue (29%, n = 13), diarrhea (18%, n=8), dry mouth (16%, n=7), and decreased appetite (11%, n=5). Hematologic AEs, regardless of relatedness, were reported in 40% of patients (n=18). Anemia was most frequent (33%, n=15), followed by neutropenia (11%, n=5) and thrombocytopenia (2%, n=1).

Twenty-six percent of the patients experienced a Grade 3 AEs (regardless of relatedness), and no Grade 4 AEs were reported. Eleven Grade 3 AEs in 9 patients (20%) were considered related to BGB-290: anemia (n=5), neutropenia (n=3), hypophosphatemia (n=1), nausea (n=1), and fatigue (n=1). Serious AEs reported as related to BGB-290 included anemia (n=2) and nausea (n=1).

The DLT of BGB-290 was persistent Grade 2 nausea despite optimal standard medical therapy observed in the 120 mg BID cohort (n=2) and in one patient each in the 40 mg and 80 mg BID cohorts. The MTD of BGB-290 was 80 mg PO BID.

Ten patients achieved either complete (n=2) or partial (n=8) responses; all responses were observed in patients with gynecological cancers, and responses were observed in the lowest dose cohorts (2.5 mg BID).

Based upon the overall safety, efficacy, and PK profile of pamiparib, the dose for further investigation was determined to be 60 mg PO BID.

1.6. Study Rationale

Alkylating agents such as TMZ cause SSBs in DNA, which leads to the recruitment of PARP1 and 2 to bind to the site of damage to repair the SSBs. PARP inhibitors are a class of drugs designed to compete at the PARP enzyme binding site and act as catalytic inhibitors, leading to accumulation of unrepaired SSBs. [60] Thus PARP inhibition enhances the cytotoxicity of the BER pathway, and therefore, enhances TMZ cytotoxicity. [6261, 62]

The study populations proposed for the expansion phase of this study are patients with tumors likely to harbor DNA damage repair deficiencies susceptible to treatment with PARP inhibitors. It is hypothesized that increased DNA damage by TMZ and PARP inhibition will provide synergism resulting in an increased anti-tumor activity in advanced solid tumors. Furthermore, the clinical data for the use of PARP inhibitors in patients with TNBC, ovarian cancer, mCRPC, gastric cancer, and SCLC discussed in Section 1.2, along with the data describing the use of PARP inhibitors plus TMZ in Section 1.3, supports evaluating pamiparib in combination with TMZ in this patient population.

1.6.1. Rationale for Dose Selection of Pamiparib

In the clinic, pamiparib has shown favorable PK properties, has been well-tolerated, and achieved maximum pharmacodynamic target modulation in PBMCs at a dose level below the regimen for this study (10 mg versus 60 mg BID). The dose of pamiparib chosen for this study is based on the recommended Phase 2 dose (RP2D) determined in the Phase 1 monotherapy study, BGB-290-AU-002, discussed in Section 1.5.

1.6.2. Rationale for Dose Selection of Temozolomide (TMZ)

As discussed in Section 1.3, previous combination studies using standard doses of TMZ and increasing low doses of PARP inhibitors had only modest anti-tumor effects and increased cytopenia. A recent study that used sub-therapeutic doses of TMZ with standard doses of talazoparib showed more promising anti-tumor effects and a better safety profile [36]. Similarly, this study is designed to use the RP2D of pamiparib (60 mg BID) with low doses of TMZ, starting from 40 mg/day up to 120 mg/day (23 mg/m²/day to 69 mg/m²/day) or higher which corresponds to 15%-46% of its recommended dose (150mg/m²/day) when administered daily for 5 days every 28 days (see Section 6.1 , Table 2). In addition, continuous dosing of TMZ will start at 40 mg/day and would potentially increase up to 120 mg/day of TMZ, which translates to 30% and 92%, respectively, of a daily dose of 75 mg/m². [56, 59]

In summary, pamiparib is a promising selective inhibitor of PARP1 and PARP2 that exhibits excellent DNA-trapping activity making it an excellent candidate to determine the effects of combining PARP inhibition with TMZ in these patient populations.

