and a dose expansion phase. The dose escalation phase of the study will evaluate the safety, tolerability, preliminary efficacy, and PK in addition to determining the MTD or MAD for the combination. In the dose expansion phase of this study, the safety, antitumor activity and PK profile of the combination will be evaluated further. Preliminary biomarkers for efficacy will also be explored through both phases of the study. The dose first phase of the study consists of a modified 3+3 dose escalation scheme utilizing a fixed dose of pamiparib in combination with escalating doses of TMZ. There will be two arms that will undergo dose escalation independently, starting with Dose Level 1. In Arm A, TMZ will be administered once a day during Days 1 to 7 of each 28-day cycle (pulsed). In Arm B, TMZ will be administered once a day continuously during each 28-day cycle. The second phase (dose expansion) of the study will further evaluate the safety and anti-tumor activity of pamiparib in combination with TMZ at the dose and schedule that will be chosen based on all data available from the dose escalation phase. The expansion phase will enroll patients in 6 different cohorts according to indication and/or homologous recombination deficiency (HRD) status as follows: Cohort 1: HRD positive (HRD+) ovarian cancer; Cohort 2: HRD+ triple-negative breast cancer (TNBC); Cohort 3: HRD+ metastatic castration-resistant prostate cancer (mCRPC); Cohort 4: ES-SCLC; Cohort 5: G/GEJ cancer; and Cohort 6: patients who have HRD+ non-squamous non-small cell lung cancer (NSCLC), squamous NSCLC, esophageal cancer, squamous head and neck cancer or soft-tissue sarcomas. Enrollment into these cohorts will occur simultaneously and independently.

It is expected that approximately 250 patients will be enrolled in the entire study. Each expansion cohort will enroll approximately 20-25 patients; cohorts might enroll additional patients based on emerging data, but the total number of patients enrolled in the study will not exceed 250 patients.

Enrollment will start at Dose Level 1 and follow the escalation scheme outlined below (interim dose levels may be tested based on available clinical and PK data).

Dose Escalation

	Arm A (Pulse Dosing of TMZ)		Arm B (Continuous Dosing of TMZ)	
Dose Level	Pamiparib Continuous	TMZ Days 1 to 7, every 28 days	Pamiparib Continuous	TMZ Continuous
-1	60 mg BID	20 mg QD	60 mg BID	20 mg QD*
1	60 mg BID	40 mg QD*	60 mg BID	40 mg QD

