4.2. Details of Dose Escalation

4.2.1. Starting Dose and Dose Escalation Approach

The dose escalation phase consists of two arms as follows:

Arm A (pulse TMZ dosing): continuous pamiparib (60 mg BID) in combination with increasing doses of TMZ (flat doses of 40, 80, 120 mg QD and higher, if tolerated) administered on Days 1 to 7 of each 28-day cycle

Arm B (continuous TMZ dosing): pamiparib (60 mg BID) in combination with increasing doses of TMZ (flat doses of 20, 40, 80, 120 mg QD and higher, if tolerated) administered continuously.

A minimum of three patients will be enrolled in Arm A, Dose Level 1, before patients are enrolled into Arm B, Dose Level 1. Subsequently, enrollment and dose escalation decisions for the two arms will occur independently of each other.

The dose for pamiparib will be the RP2D of 60 mg PO BID ('full-dose' pamiparib) based on the rationale outlined in Section 1.6. Since TMZ is given as a DNA-damaging sensitizer for pamiparib and to simplify TMZ dosing, flat-dosing will be used for TMZ. The first dose level of 40 mg QD corresponds to 23 mg/m² assuming an average body surface area of 1.73 m². Subsequent dose levels of 80 mg and 120 mg correspond 46 mg/m² and 69 mg/m², respectively. Additional higher dose levels may be explored, and the TMZ dose will not be increased by more than 50% each time nor will it exceed the approved daily dose at the corresponding schedule.

Once the MTD has been determined in Arm A (pulse dosing) and taking into consideration all data available for Arm B at that time, further dose escalation may be pursued for Arm A by extending the time window of TMZ administration by no more than one additional week per dose escalation step. For example, TMZ administration at the MTD dose level may be extended to Days 1 to 14 and then to Days 1 to 21 following dose escalation rules outlined in Section 4.2.2.

If the MTD is exceeded with the starting dose of TMZ, then a dose level of 20 mg QD TMZ (Dose Level -1) may be explored. (Table 1).

Table 1: Dose Escalation Scheme for Pamiparib plus TMZ

	Arm A (Pulse Dosing of TMZ)		Arm B (Continuous Dosing of TMZ)	
Dose Level	Pamiparib Continuous	TMZ Days 1 to 7, every 28 days	Pamiparib Continuous	TMZ Continuous
-1	60 mg BID	20 mg QD	60 mg BID	20 mg QD*
1	60 mg BID	40 mg QD*	60 mg BID	40 mg QD
2	60 mg BID	80 mg QD	60 mg BID	80 mg QD
3	60 mg BID	120 mg QD	60 mg BID	120 mg QD

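### The protocol gives two incompatible starting doses of temozolomide for Arm B, 20 mg and 40 mg once daily, and the fallback and stagger rules depend on which applies.

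*Protocol*

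**What the plan says.** In both arms, the synopsis table and Table 1 define Dose Level -1 as 20 mg once daily and Dose Level 1 as 40 mg.

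**Places that indicate a 40 mg start for Arm B**
- Section 1.6.2: "continuous dosing of TMZ will start at 40 mg/day", with a range up to 120 mg/day, "which translates to 30% and 92%, respectively, of a daily dose of 75 mg/m²".
- Synopsis, Study Design: "There will be two arms that will undergo dose escalation independently, starting with Dose Level 1". A later synopsis sentence also has enrollment begin at Dose Level 1.
- Section 4.2.1 calls 40 mg once daily the first dose level and converts it to 23 mg/m².

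**Places that indicate a 20 mg start for Arm B**
- Section 4.2.1 lists Arm B as "flat doses of 20, 40, 80, 120 mg QD and higher, if tolerated) administered continuously". The Arm A list reads "flat doses of 40, 80, 120 mg QD and higher, if tolerated".
- The synopsis table and Table 1 both put the starting-dose asterisk on 20 mg (Dose Level -1) for Arm B and on 40 mg (Dose Level 1) for Arm A.

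**Rules that depend on the start (Section 4.2.1)**
- Stagger: "A minimum of three patients will be enrolled in Arm A, Dose Level 1, before patients are enrolled into Arm B, Dose Level 1".
- Fallback: "If the MTD is exceeded with the starting dose of TMZ, then a dose level of 20 mg QD TMZ", labelled Dose Level -1, may be explored. The sentence is not limited to Arm A.

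**The concern.** The starting dose of an escalation arm should have one value. Here the synopsis text disagrees with the synopsis table, and Section 4.2.1 disagrees with itself. An error of extraction from the PDF is an unlikely explanation: the asterisk sits on the same cell in two tables, and the separate Arm B dose list also begins at 20 mg.

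The stakes are first the safety of the first patients on continuous dosing. Section 1.3 reports myelosuppression as dose-limiting in the earlier combination studies that used standard temozolomide doses, and Cycle 1 is the window for dose-limiting toxicity (DLT). Second, two safety rules take their meaning from the starting level. Third, the maximum tolerated or administered dose is a primary objective, so the record should show one planned start for each arm.

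**Working it through.** **Inputs.** Average body surface area 1.73 m² (Section 4.2.1 and Table 2); reference daily dose 75 mg/m² (Section 1.6.2); flat doses 20, 40 and 120 mg (Table 1); 28-day cycle with temozolomide every day in Arm B.

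**Step 1. Reproduce the percentages in Section 1.6.2.** Formula: flat dose / 1.73 / 75.
- 40 mg: 40 / 1.73 = 23.1 mg/m²; 23.1 / 75 = 30.8%. From the rounded 23.0 in Table 2 it is 30.7%. The plan states 30%, apparently truncated.
- 120 mg: 120 / 1.73 = 69.4 mg/m²; 69.4 / 75 = 92.5%. From the rounded 69.0 it is 92.0%. The plan states 92%.

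The figures reproduce to within one percentage point, so the rationale was calculated for a 40 mg start.

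**Step 2. The same calculation at the dose marked in Table 1.**
- 20 mg: 20 / 1.73 = 11.6 mg/m² (Table 2 gives 11.5); 11.6 / 75 = about 15%.

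The stated 30% cannot describe a 20 mg start.

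**Step 3. Size of the gap.**
- Ratio: 40 / 20 = 2.0.
- Planned temozolomide in one cycle: 28 x 20 = 560 mg against 28 x 40 = 1120 mg.

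**Step 4. Each rule under each reading.**

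| | Arm B starts at 40 mg (Level 1) | Arm B starts at 20 mg (Level -1) |
|---|---|---|
| Fallback to 20 mg | Step down of 40 - 20 = 20 mg | Step down of 20 - 20 = 0 mg |
| Stagger before Arm B Level 1 | Covers the first Arm B patients | Does not cover patients entering at Level -1 |
| 30% figure in Section 1.6.2 | Consistent | Inconsistent (about 15%) |

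For Arm A the asterisk is on 40 mg, so the fallback is a real step from 40 to 20 mg and raises no question.

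**The case against.** **The Arm B start may already be history.** The Schedule of Assessments (Appendix 1 Table 1) names a recommended dose for expansion, 60 mg once daily on Days 1 to 7 of each cycle. Table 2 lists 60 mg, a level absent from Table 1. The SAP overview puts the two-arm escalation plan in the past tense. By Section 4.3 the expansion dose and schedule are chosen after the escalation cohorts are reviewed. A reader might infer from the contradiction that sites will now give different first doses, but on this evidence that prospective risk is weak. It is not excluded, because much of the escalation text is still in the future tense. This objection stands and lowers the urgency.

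**DLT data would not be mixed across levels.** A reader might infer that they would be. The documents do not support this. Each level label maps to one dose in both tables, and DLTs are reported by combination dose level (Protocol Section 11.3.2, SAP Section 6.4.2). A patient given 20 mg counts at 20 mg whichever level came first.

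**Arm B is not left without a way down.** A reader might infer this from the fallback sentence. But the synopsis allows interim dose levels, the text after Table 1 allows alternative regimens, and Section 4.2.2 allows a lower or intermediate level. What is missing under a 20 mg start is narrower: no temozolomide level below 20 mg is named.

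**The stagger rule does not itself state a starting dose.** That is correct. It can work as a gate on the 40 mg level even if Arm B had an earlier 20 mg level. It is therefore not counted here as evidence for a 40 mg start, only as a rule whose coverage depends on the answer.

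**Conclusion.** The point holds as an internal inconsistency in current protocol text. The two Arm B starting doses differ by a factor of two (560 against 1120 mg planned per 28-day cycle), and no passage reconciles them. If the tables govern, the fallback sentence offers Arm B no named temozolomide step down, the stagger does not cover its first patients, and the 30% in Section 1.6.2 is about double the true share. If the text on 40 mg governs, the tables and the Arm B dose list are wrong.

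The milligram totals assume every daily dose of the cycle is taken; the percentages assume the protocol's own average body surface area. Neither assumption affects the two-fold ratio. No effect on any estimate is claimed. The passages must be reconciled because a starting dose and two safety rules depend on them, with less urgency if Arm B has already opened.

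**What to change.** Reconcile Section 1.6.2, the dose list and text of Section 4.2.1, Table 1, and the synopsis text and table so that they all state one Arm B starting level. Then:
- Bring the percentage in Section 1.6.2 into line with that level.
- Reword the stagger rule to refer to the level at which Arm B opens.
- Reword the fallback sentence arm by arm, so that it does not name an arm's own starting dose as its reduction, or refer to the general provisions where no lower level is named.
- If Arm B has already opened, record the level actually used as its start and report it in the study report.

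This review takes no position on which dose is right. The cost is protocol wording only; sample size and analyses do not change.

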1.7. Risk-Benefit Assessment

Pamiparib has been studied in nonclinical toxicity and Phase 1 clinical studies. Pamiparib toxicities are largely consistent with the safety profile shared by other PARP inhibitors with the important exception that pamiparib may cause less myelosuppression. PARP inhibitors, including pamiparib, show a partial overlap with the safety profile of TMZ. Therefore, patients of this study may experience AEs typical for these study drugs at a higher frequency and/or severity. In addition, patients may encounter AEs that are uniquely caused by the novel combination(s). However, with the lower doses of TMZ being used in this study, it is possible there could be fewer myelosuppressive-related AEs than previously seen in other studies using TMZ in combination with PARP inhibitors.

Myelodysplastic syndrome and acute myeloid leukemia (AML) have been reported in a small number (< 1%) of patients treated with PARP inhibitors, especially in patients harboring a germline *BRC A* mutation. [63] Typically, patients who develop MDS and AML while on PARPi therapy had a history of extensive previous chemotherapy and some had a history of previous cancer or bone marrow abnormalities. To date, there have been no reports of MDS or AML in patients treated with pamiparib and no fatal drug reactions. Patients in this study will be monitored monthly for hematological toxicities and events of MDS and AML will be reported as serious AEs (SAEs).

Preliminary data show that pamiparib appears to be generally well tolerated in patients with advanced solid tumors. The safety profile for single-agent pamiparib is similar to that of other PARP inhibitors. Given the dire prognosis of the patients that will be enrolled in this study and

the limited treatment options, the risk of combining pamiparib with TMZ appears acceptable in the context of a Phase 1 study with close monitoring through AE reporting, recording of vital signs and ECGs, clinical laboratory testing, and tumor assessments. As outlined in Section 1.1 and Section 1.6, scientific rationale and supportive data are strong for combining PARP inhibitors with TMZ in TNBC, ovarian cancer, mCRPC, and other solid tumors with homologous recombination deficiency as well as in SCLC and gastric cancer.

1.8. Study Conduct

This study will be conducted in compliance with the protocol approved by the Institutional Review Board (IRB) or Independent Ethics Committee (IEC), and in accordance with Good Clinical Practice (GCP) standards.

2. STUDY OBJECTIVES

2.1. Primary Objectives

- To determine the safety and tolerability of pamiparib when given orally in combination with temozolomide (TMZ; pulsed and continuous)
- To determine the maximum tolerated dose (MTD) or maximum administered dose (MAD) for pamiparib combined with TMZ (pulsed and continuous)
- To select the recommended Phase 2 dose and schedule of pamiparib in combination with TMZ
- To determine the antitumor activity of pamiparib in combination with TMZ

2.2. Secondary Objectives

- To characterize the pharmacokinetics (PK) of pamiparib and TMZ

2.3. Exploratory Objectives

- To evaluate candidate biomarkers in tumor tissue and in peripheral circulation as potential markers of response, resistance, or disease progression

3. STUDY ENDPOINTS

3.1. Primary Endpoints

- Dose Escalation Phase: Incidence and nature of DLTs
- Incidence, nature, and severity of AEs, graded according to the National Cancer Institute Common Terminology Criteria for Adverse Events (NCI CTCAE), v4.03
- Objective response rate (ORR), as assessed using RECIST v1.1

3.2. Secondary Endpoints

- Pharmacokinetic parameters of pamiparib and TMZ, including but not limited to C_{trough}
- Time-to-event endpoints, e.g., duration of response (DOR), disease control rate (DCR), progression free survival (PFS), and overall survivals (OS)

3.3. Exploratory Endpoints

- Candidate predictive biomarkers, including, but not limited to expression and mutations of genes in the DNA damage response pathway and relationship to efficacy and resistance

4. STUDY DESIGN

4.1. Summary of Study Design

This is an open-label, multi-center Phase 1b study to evaluate the combined use of pamiparib, a PARP inhibitor, with a DNA-alkylating agent, TMZ, in patients with locally advanced and metastatic solid tumors. The study consists of a dose escalation phase and a dose expansion phase. The dose escalation phase of the study will evaluate the safety, tolerability, preliminary efficacy, and PK, in addition to determining the MTD and/or MAD for the combination. In the dose expansion phase of this study, the safety, preliminary efficacy, and PK profile of the combination will be further evaluated in specific patient populations. Preliminary biomarkers for efficacy will also be explored during both phases of the study.

Dose Escalation:

The dose escalation phase of the study consists of a modified 3+3 dose escalation scheme utilizing a fixed dose of pamiparib in combination with escalating doses of TMZ. There will be two arms that will undergo dose escalation independently. In Arm A, TMZ will be administered once a day during Days 1 to 7 of each 28-day cycle (pulsed). In Arm B, TMZ will be administered once a day continuously during each 28-day cycle.

Dose Expansion:

The dose expansion phase of the study will further evaluate the safety and anti-tumor activity of pamiparib in combination with TMZ at the dose and schedule that will be chosen based on all data available from the dose escalation phase.

It is expected that approximately 250 patients will be enrolled in the entire study. Patients will be enrolled in 6 different cohorts based on their disease characteristics and/ or HRD status as described in Section 4.3; Enrollment into these cohorts will occur simultaneously and independently of each other. Each expansion cohort will enroll up to 20-25 patients each and may enroll additional patients based on emerging data, but the total patients enrolled in the study will not exceed 250 patients.

Adverse events (AEs) that occur during and after the treatment period with study drug(s) will be followed and documented as outlined in Section 7.4 and Section 10. AEs will be graded according to NCI CTCAE v4.03.

Pharmacokinetic analysis will be performed for both pamiparib and TMZ during Cycle 1. Biomarker analysis will include but is not limited to germline *BRCA1/2* mutations, DNA HRD status, and somatic mutation analysis.

Anti-tumor activity will be evaluated by the treating investigator using standard RECIST v1.1 criteria (Appendix 5). Tumor response will also be evaluated according to the Gynecologic Cancer Intergroup (GCIg) criteria for patients with ovarian cancer. In addition, the Prostate Cancer Clinical Trials Working Group 2 (PCWG2) criteria will be used for patients with prostate cancer.

Patients who, at the time of progression, have an ongoing AE that leads to treatment discontinuation, will be followed until the event resolves, the investigator assesses the event as stable, the patient is lost to follow-up, or the patient starts a different anti-tumor therapy. If a patient discontinues study drug due to reasons other than disease progression or death, then tumor assessments should continue to be performed following the scheduled assessment plan until the start of new anticancer therapy, disease progression, death, lost to follow-up, or withdrawal of consent to efficacy follow-up.

In the absence of unacceptable toxicities or disease progression, patients will be offered continued study treatment of BGB-290 plus TMZ. Regardless of discontinuation of one or more study drugs, patients should continue on study with regular follow-up (Section 8.5). Patients who have discontinued all study drugs should return to the clinic for an end-of-treatment (EOT) visit within 7 days after the last study treatment (Section 8.4). After the EOT visit, patients should have regular follow-up for safety, efficacy, and survival as outlined in Section 8.5.

Study procedures and assessments are further detailed in Section 7 and Section 8, and a Schedule of Assessments can be found in [Appendix 1 Table 1](#).

